4.1.2 Exclusion Criteria

Patients who meet any of the following criteria will be excluded from study entry:

- History of a severe allergic reaction or anaphylactic reaction to a biologic agent or known hypersensitivity to any component of the lebrikizumab injection
- Evidence of other known causes of ILD (e.g., domestic and occupational environmental exposures, connective-tissue disease [CTD], and drug toxicity)
- Lung transplant expected within 12 months of screening
- Evidence of clinically significant lung disease other than IPF (e.g., asthma or COPD)
- Post-bronchodilator forced expiratory volume in 1 second (FEV₁)/FVC ratio < 0.7 at screening
- Positive bronchodilator response evidenced by an increase of $\geq 12\%$ predicted and 200 mL increase in either FEV₁ or FVC

- Any clinically significant medical disease (other than IPF) that is associated with an expected survival of < 12 months, likely to require a change in therapy during the study, or likely to impact the ability of the patient to participate in the study in the opinion of the investigator, or impact the study efficacy or safety assessments
- Requirement for continuous medical care and assistance or limited ability to self-care that would impact the ability of patient to participate in the study or to perform the study-related assessments
- Class IV New York Heart Association chronic heart failure or historical evidence of left ventricular ejection fraction < 35%
- Hospitalization due to an exacerbation of IPF within 4 weeks prior to or during screening
- Known current malignancy or current evaluation for a potential malignancy
- Major episode of infection requiring any of the following:
 - Admission to the hospital for ≥ 24 hours within 4 weeks prior to screening or during screening and run-in period
 - Treatment with antibiotics (IV, IM, oral, or inhaled) within 4 weeks prior to screening or during screening and run-in period
- An active upper or lower respiratory tract infection occurring at any time within the screening period prior to the randomization visit (Visit 1 to Day 1, Visit 2)
- *Listeria monocytogenes* infection or active parasitic infection within 6 months prior to Day 1, Visit 2
- Active tuberculosis requiring treatment within 12 months prior to screening
- Known immunodeficiency, including but not limited to HIV infection
- Past use of any anti-IL-13 or anti-IL-4/IL-13 therapy, including lebrikizumab
 - Patients participating in a clinical trial that has not been unblinded should be assumed to have received the active drug
- Evidence of acute or chronic hepatitis or known liver cirrhosis
- AST, ALT, or total bilirubin elevation $\geq 2.0 \times$ the upper limit of normal during screening
- Clinically significant abnormality on ECG at screening or laboratory tests (hematology, serum chemistry, and urinalysis) that, in the opinion of the investigator, may pose an additional risk in administering study drug to the patient
- Receipt of a live/attenuated vaccine within the 4 weeks prior to Visit 1
- Chronic treatment with any of the following within 4 weeks or five half-lives prior to screening (whichever is longer) to the end of the placebo-controlled period (Day 365, Visit 16):
 - Immunosuppressive or immunomodulatory therapies (e.g., azathioprine, cyclosporine A, cyclophosphamide, D-penicillamine, interferon-gamma, tumor necrosis factor- α antagonists)

Cytotoxic drugs (e.g., colchicine) if used for IPF indication

Pirfenidone (Exclusion Limited to Cohort A)

N-acetylcysteine

Pulmonary hypertension therapies (e.g., endothelin receptor antagonist, phosphodiesterase type-5 inhibitor, riociguat, prostacyclin or prostacyclin analogue)

Tyrosine kinase inhibitors including exclusion of nintedanib for Cohort A and Cohort B

Warfarin or other anticoagulant therapy if given for IPF indication

Any unlicensed therapy given for the indication of IPF

Any investigational agent

- Chronic oral corticosteroid therapy is not permitted within 4 weeks prior to screening (Visit 1), during screening and run-in, *or throughout the study* period
- History of alcohol, drug, or chemical abuse that would impair or risk the patient's full participation in the study, in the opinion of the investigator
- Female patients of reproductive potential who are not willing to use a highly effective method of contraception (e.g., contraceptive pill or transdermal patch, spermicide and barrier [i.e., condoms], intrauterine device, implants for contraception, injections for contraception [with prolonged release], hormonal vaginal device, sterilization, surgical tubal ligation) for the duration of the study and for at least 18 weeks after the last dose of lebrikizumab or placebo study treatment) (see [Appendix 9](#))
- Pregnant or lactating
- Body weight < 40 kg

4.1.2.1 Additional Exclusions Limited to Cohort B (Pirfenidone Background)

- Known achalasia, esophageal stricture, or esophageal dysfunction sufficient to limit the ability to swallow oral medication
- Tobacco smoking or use of tobacco-related products within 3 months of screening or unwillingness to avoid smoking throughout the study (e.g., cigarette, pipe, cigar)
- Any condition that, as assessed by the investigator, might be significantly exacerbated by the known side effects associated with pirfenidone
- Known or suspected peptic ulcer
- Creatinine clearance < 40 mL/min, calculated using the Cockcroft-Gault formula
- Ongoing use of the following therapies or agents within 4 weeks of randomization (Day 1, Visit 2), or during the study

Strong inhibitors of CYP1A2 (e.g., fluvoxamine or enoxacin)

Moderate inducers of CYP1A2, limited to tobacco smoking and tobacco-related products

4.2 METHOD OF TREATMENT ASSIGNMENT AND BLINDING

Patients will be randomized to the treatment arms through the interactive voice/Web-based response system (IxRS). After written informed consent has been obtained, all patients will receive a screening number, which will be assigned by the IxRS. Following completion of the screening period and after all patient eligibility requirements are confirmed on Day 1, patients will be assigned an identification number (a different number from the screening number) and will be randomized in a 1:1 ratio to one of two treatment arms (**Cohort A** - lebrikizumab 250 mg SC or placebo SC every 4 weeks; **Cohort B** - lebrikizumab 250 mg SC and pirfenidone \leq 2403 mg/d or placebo SC every 4 weeks and pirfenidone \leq 2403 mg/d) for the 52-week placebo-controlled study period. Patients will be randomized on the same day that treatment is to be initiated (Day 1, Visit 2). Dynamic hierarchical randomization will be performed centrally and stratified by region (United States, Europe/Canada, other), lung function (FVC $<$ 50%, 50% to 75%, $>$ 75% predicted), and serum periostin concentration ($<$ 50 ng/mL, \geq 50 ng/mL) within each cohort. During the placebo-controlled study period and the open-label lebrikizumab treatment period, the IxRS will make study treatment kit assignments. IxRS will also make pirfenidone treatment kits available for patients in Cohort B. At each dosing visit during the placebo-controlled period, study treatment kits will be assigned for administration. The placebo and active kits are filled and packaged to look identical. Patient randomization and the study treatment kit assignments will be verified on an ongoing basis by an external and independent statistical coordinating center to ensure that randomization and kit assignments are conducted correctly by the IxRS.

Patients, all study site personnel, and the Sponsor and its agents (with the exception of the IxRS service provider, the external independent statistical coordinating center responsible for verifying patient randomization and study treatment kit assignments, PK/PD laboratory personnel, the iDMC and iDCC members) will be blinded to treatment assignment throughout the placebo-controlled period. As described in Section 6, treatment assignment will be unblinded to the personnel performing the analysis when all data for the primary endpoint period are in the database and the data have been cleaned and verified. [REDACTED]

[REDACTED] However, patients and all study site personnel will remain blinded to individual treatment assignment until after the study is completed (after all patients have either completed the safety follow-up period or discontinued early from the study), the database is locked, and the study analyses are final.

If unblinding is necessary for patient management (in the case of a serious adverse event), the investigator will be able to break the treatment code by contacting the IxRS. Treatment codes should not be broken except in emergency situations. If the investigator wishes to know the identity of the study treatment for any other reason, he or she should contact the Medical Monitor directly. The investigator should document

and provide an explanation for any premature unblinding (e.g., accidental unblinding or unblinding because of a serious adverse event).

As per health authority reporting requirements, Roche will break the treatment code for all unexpected serious adverse events (see Section 5.7) that are considered by the investigator to be related to study drug.

4.3 STUDY TREATMENT

4.3.1 Formulation, Packaging, and Handling

4.3.1.1 Lebrikizumab and Placebo

[REDACTED]

For further details, see the Lebrikizumab IB.

4.3.2 Pirfenidone/Background Treatment in Cohort B

ESBRIET (pirfenidone) is approved in a 267-mg capsule dosage form. The recommended dose is 801 mg (i.e., three 267-mg capsules) TID, at the same times each day, taken with food (total dose, 2403 mg/d) (Section 4.3.4). ESBRIET is packaged in a 250-cc HDPE bottle. For information on the formulation, packaging, and handling of pirfenidone see the local prescribing information for ESBRIET or PIRESPA in Japan or the pirfenidone IB. For patients treated with PIRESPA (limited to Japan), dose titration and management of adverse effects should be based upon guidance in the marketed product label including a maximum recommended dose ≤ 1800 mg/d. Investigators are advised to follow the country specific guidance for dose titration and handling.

Pirfenidone, licensed as ESBRIET or PIRESPA, may be locally sourced for patients with access through their healthcare provider until it is provided by the Sponsor as IMP through the IxRS system.

4.3.3 Dosage, Administration, and Compliance

4.3.3.1 Lebrikizumab and Placebo (Cohort A)

Patients in Cohort A and Cohort B who meet all eligibility criteria will be randomly assigned to receive lebrikizumab 250 mg or placebo Q4W for the 52-week placebo controlled period.

Treatment with lebrikizumab or placebo will be by SC injection in the arm, thigh, or abdomen. All patients will receive a total of two injections per dosing visit. Each injection should be administered in a separate location at least 10 cm from the other injection site at each dosing visit. Study sites will be asked to record each injection site. Patients will be monitored for a minimum of 1 hour after dosing for the first three treatment visits and for 30 minutes for all subsequent treatment visits. Each patient will receive a minimum of 13 doses (2 injections per dose) of study treatment during the placebo-controlled, blinded, study treatment period. Patients in Cohort A who enrolled in the study prior to this amendment may receive up to 31 doses of blinded study treatment based upon previous version of this protocol. No dosage modification is permitted during the study.

Patients in **Cohort A** will receive an additional 52 weeks of open-label lebrikizumab (13 doses) in the open-label lebrikizumab treatment period after completion of the placebo controlled period.

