3. STUDY DESIGN

3.1 DESCRIPTION OF STUDY

3.1.1 Overview of Study Design

This is a randomized, multicenter, double-blind, placebo-controlled, parallel-group study of lebrikizumab in patients with IPF. Approximately 480 patients with a diagnosis of IPF will be enrolled in the study across two cohorts (approximately 150 patients in Cohort A having approximately 75 patients per treatment arm and approximately 330 patients in Cohort B having approximately 165 patients per treatment arm) at approximately 120 sites located globally. The total treatment duration will be based on all patients receiving at least 13 doses (one dose every 4 weeks [Q4W]) of blinded treatment over 48 weeks. The study primary endpoint will measure the absolute change from baseline to Week 52 in percentage of predicted FVC.

Two cohorts of patients will be enrolled in the study; Cohort A patients will be treated in the absence of pirfenidone IPF background therapy; Cohort B patients will be treated with pirfenidone as background therapy.

Cohort A (monotherapy) approximately 150 patients will be randomized 1:1 to lebrikizumab (250 mg SC) every 4 weeks or placebo in the absence of background IPF therapy.

Cohort B (combination therapy) approximately 330 patients will be treated daily with the maximum tolerated dose of pirfenidone ≤ 2403 mg/d, and randomized 1:1 to either lebrikizumab (250 mg SC) every 4 weeks or placebo.

Patients who provide written informed consent will commence a screening period, which will last 28 days (± 14 days) to establish entry criteria. During the screening period, patients will have their IPF diagnosis (i.e., HRCT \pm surgical lung biopsy [SLB]) confirmed by central review based upon the 2011 ATS/ERS/JRS/ALAT guidelines.

For Cohort B/combination therapy, patients may initiate screening on a stable dose of pirfenidone or free of background IPF therapy. After completing the initial screening assessments ($28d \pm 14d$), eligible patients who are naive or not currently treated with pirfenidone will initiate the pirfenidone titration run-in period (4-6 weeks) with Visit 1.5 to allow for titration of pirfenidone to a dose of 2403/mg/d as per label (three 267 mg capsules three times a day [9 capsules daily] with food for a total of 2403 mg/day) or to the highest dose tolerated or recommended dose per country specific guidelines (see Section 4.3.4). Patients who are unable to complete the titration run-in period will be considered run-in failures.

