All patients will return to the clinic approximately 4 weeks after their last dose of study drug to complete follow-up assessments at the end-of-treatment (EOT) visit (see [Appendix 1](#), [Appendix 2](#), and [Appendix 3](#)). All patients will be followed-up for 18 weeks after the last dose including two subsequent visits during a 14-week safety follow-up period as indicated in schedule of assessments (see [Appendix 4](#)). Patients who choose to prematurely discontinue study drug will be encouraged to remain in the study and complete all remaining assessments. If this is not feasible, the patient should enter and complete the safety follow-up period unless consent has been withdrawn.

Measures of safety and efficacy will be assessed throughout the study as detailed in the schedule of assessments (see [Appendix 1](#), [Appendix 2](#), [Appendix 3](#), and [Appendix 4](#)). The primary efficacy outcome measure for this study is the absolute change from baseline to Week 52 in percentage of predicted FVC. A key secondary outcome will be PFS measured as the time from randomization to disease progression or death (see Section 2.2 and Section 3.3.1.1 for details). All other secondary and exploratory efficacy outcomes will be measured at Week 52 and at various other timepoints throughout the study.

A schedule of assessments is provided in [Appendix 1](#), [Appendix 2](#), [Appendix 3](#), and [Appendix 4](#) and a study schema is provided in [Figure 1](#).

[figure not shown]
Figure 1 Study Schematic

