3.2 END OF STUDY

The end of the study is defined as the date when the last patient, last visit (LPLV) occurs. The LPLV is expected to occur a maximum of 118 weeks after the last patient is enrolled and randomized into Cohort A. This timeframe includes a 52-week placebo-controlled period and a maximum of an additional 52 week open-label lebrikizumab treatment period followed by the safety follow-up period. In the case that enrollment in Cohort B is slower than anticipated, LPLV is expected occur a maximum of 66 weeks after the last patient is enrolled and randomized into Cohort B. This timeframe includes a 52-weeks placebo-controlled period followed by the safety follow-up period. All patients will be followed for safety for 18 weeks after the last dose of study treatment of lebrikizumab or placebo by SC injection.

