Day (Assessment Window)	365 (1OL) (± 3)	393 (29OL) (± 3)	421 (57OL) (± 3)	449 (85OL) (± 3)	477 (13OL) (± 3)	505 (141 OL) (± 3)	533 (169 OL) (± 3)	561 (197 OL) (± 3)	589 (225 OL) (± 3)	617 (253 OL) (± 3)	645 (281 OL) (± 3)	673 (309 OL) (± 3)	701 (337 OL) (± 3)	729 (365 OL) (± 3)		
Visit	35	36	37	38	39	40	41	42	43	44	45	46	47	EoT ^b /SFU Wk4	ET ^q	UV
Hematology ^g		x	x		x		x		x		x		x	x	x	x
Chemistry ^h		x	x		x		x		x		x		x	x	x	x
Urinalysis ⁱ		x	x		x		x		x		x		x	x	x	
Urine pregnancy ^j		x	x	x	x	x	x	x	x	x	x	x	x	x	x	
Serum PK ^k				x			x			x				x	x	
Plasma PD sample ^{k,l}		x	x	x			x			x			x	x	x	x
Serum PD ^{k,l}		x	x	x			x			x			x	x	x	x
Serum antibodies ^k		x		x			x							x	x	
Serum Tryptase ^m																
Optional RNA ⁿ				x			x							x		
Study drug administration ^{o,p}	x	x	x	x	x	x	x	x	x	x	x	x	x	x		
Concomitant medications ^q		x	x	x	x	x	x	x	x	x	x	x	x	x	x	x

Appendix 2

Schedule of Assessments: Open-Label Lebrikizumab Treatment Period - Cohort A (cont.)

Week	Wk 52 (Day1 OL)	Wk 56 (Wk4 OL)	Wk 60 (Wk8 OL)	Wk 64 (Wk12 OL)	Wk 68 (Wk16 OL)	Wk 72 (Wk20 OL)	Wk 76 (Wk24 OL)	Wk 80 (Wk28 OL)	Wk84 (Wk32 OL)	Wk 88 (Wk36 OL)	Wk92 (Wk40 OL)	Wk96 (Wk44 OL)	Wk100 (Wk48 OL)	Wk104 (Wk52 OL)		
Day (Assessment Window)	365 (1OL) (± 3)	393 (29OL) (± 3)	421 (57OL) (± 3)	449 (85OL) (± 3)	477 (13OL) (± 3)	505 (141 OL) (± 3)	533 (169 OL) (± 3)	561 (197 OL) (± 3)	589 (225 OL) (± 3)	617 (253 OL) (± 3)	645 (281 OL) (± 3)	673 (309 OL) (± 3)	701 (337 OL) (± 3)	729 (365 OL) (± 3)		
Visit	35	36	37	38	39	40	41	42	43	44	45	46	47	EoT ^b /SFU Wk4	ET ^d	UV
Adverse events ^{a,q}		x	x	x	x	x	x	x	x	x	x	x	x	x	x	x

6MWT=six minute walk test; ATAQ-IPF= A Tool to Assess Quality of Life in IPF; Borg CR10 Scale = Borg Category Ratio 10 Scale[®]; CTD=connective-tissue disease; DL_{CO}=diffusion capacity of the lung for carbon monoxide; eCRF=electronic Case Report Form; EOMT=end of minimum treatment; EOT=end of treatment; EQ-5D=EuroQol 5-Dimension Questionnaire; ET=early termination; FEV₁=forced expiratory volume in 1 second; FVC=forced vital capacity; HRCT=high-resolution computed tomography; IL-13=interleukin 13; IPF=idiopathic pulmonary fibrosis; PD=pharmacodynamic; PK=pharmacokinetic; Rand.=Randomization; SGRQ=St. George's Respiratory Questionnaire; UV=unscheduled visit.

Notes: On treatment days, all assessments should be performed prior to dosing unless otherwise specified.

^a New or worsening abnormalities should be recorded on the Adverse Event eCRF.

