^b This visit replaces Safety Follow-up Visit 1 on [Appendix 4](#). The next visit is Safety Follow-up Visit 2 at Week 12 (12 weeks after last dose of study drug).

^c Respiratory rate, pulse rate, systolic and diastolic blood pressure while the patient is in a seated position, and temperature.

^d ECGs should be performed prior to any scheduled study procedures (e.g., vital sign measurements, blood draws, and study drug administration, if applicable).

^e The Borg CR10 Scale will be performed immediately before and after the 6MWT.

^f Complete before all other non-PRO assessments and before the patient receives any disease-status information or study treatment during the study visit.

Appendix 2

Schedule of Assessments: Open-Label Lebrikizumab Treatment Period - Cohort A (cont.)

- ^g Includes RBC count, WBC count, hemoglobin, hematocrit, platelet count, and WBC differential count (neutrophils, bands, lymphocytes, eosinophils, basophils, monocytes, and other cells).
- ^h Includes sodium, potassium, chloride, bicarbonate, glucose, BUN, creatinine, calcium, phosphorus, magnesium, total and direct bilirubin, total protein, albumin, ALT, AST, LDH, alkaline phosphatase, creatinine phosphokinase, and uric acid. Any patient who starts rescue therapy (including but not limited to pirfenidone) will need monitoring per the prescribing information. All safety laboratory assessments, including those required for the prescribed rescue medication, should be analyzed by the central laboratory utilized for the GB28547 clinical study.
- ⁱ Includes protein, blood, glucose, and microscopic examination (RBC, WBC, casts, and crystals).
- ^j Only for women of childbearing potential see [Appendix 9](#).
- ^k On dosing days. Samples for serum PK, PD, antibody (including anti-therapeutic antibody), and optional PAXgene mRNA analysis will be taken prior to dosing. An additional sample for serum antibody and PK analysis must be taken in the event of an anaphylactic, anaphylactoid, or serious hypersensitivity reaction. PLB2 antibody testing may be performed as appropriate using serum samples collected at pre-specified timepoints.
- ^l Includes IL-13 or IPF-related biomarkers (e.g., periostin, CCL18, YKL40, COMP, OPN, CCL13).

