Appendix 4 Schedule of Assessments: Safety Follow-Up Period

WEEK post last dose	4 ^a	12	18 (final visit)
Day post last dose (assessment window)	28 (± 3)	84 (± 3)	126 (± 3)
Visit	SFU1	SFU2	SFU3
Limited physical exam ^b	x		x
Weight	x		x
Vital signs ^c	x	x	x
Resting pulse oximetry	x	x	x
Single ECG (all patients) ^d	x		x
Spirometry ⁱ	x	x	x
DLco	x	x	x
6MWT/BorgCR10 ^e	x		
ATAQ-IPF ^f	x		x
SGRQ ^f	x		x
EQ-5D ^f	x		x
Hematology ^g	x	x	x
Chemistry ^h	x	x	x
Urinalysis ⁱ	x		
Urine pregnancy test ^j	x		
Serum PK sample ^k	x	x	x
Plasma PD sample ^{k,l}	x	x	x
Serum PD sample ^{k,l}	x	x	x
Serum antibodies ^k	x		x

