Appendix 4 Schedule of Assessments: Safety Follow-Up Period (cont)

WEEK post last dose	4 ^a	12	18 (final visit)
Day post last dose (assessment window)	28 (± 3)	84 (± 3)	126 (± 3)
Visit	SFU1	SFU2	SFU3
Optional RNA sample ^m	x		
Concomitant medications	x	x	x
Adverse events ^{a,n}	x	x	x
PFD dispensing (Cohort B only)	x	x	

[figure not shown]
6MWT=6-minute walk test; ATAQ-IPF=A Tool to Assess Quality of Life in IPF; Borg CR10=Borg Category Ratio 10 Scale®; DL_{CO}=diffusion capacity of the lung for carbon monoxide; ECG=electrocardiogram; EOT=end of treatment; EQ-5D=EuroQol 5-Dimension Questionnaire; ET=early termination; HRCT=high-resolution computed tomography; IPF=idiopathic pulmonary fibrosis; SGRQ=St. George's Respiratory Questionnaire; UV=unscheduled visit.

[figure not shown]
- ^a For patients in Cohort A who only complete the placebo controlled study period at Week 52 and choose to discontinue, the Week 52 visit will count as this visit. For patients in Cohort A who complete the open-label lebrizumab study period at week 52OL, the Week 52OL will count as this visit. For patients in Cohort B who complete the placebo controlled study period at Week 52, the Week 52 visit will count as this visit.
- ^b New or worsening abnormalities should be recorded on the Adverse Event eCRF.
- ^c Respiratory rate, pulse rate, systolic and diastolic blood pressure while the patient is in a seated position, and temperature.
- ^d ECGs should be performed prior to any scheduled study procedures (e.g., vital sign measurements, blood draws, and study drug administration, if applicable).
- ^e The Borg CR10 Scale will be performed immediately before and after the 6MWT.
- ^f Complete before all other non-PRO assessments and before the patient receives any disease-status information or study treatment during the study visit.
- ^g Includes RBC count, WBC count, hemoglobin, hematocrit, platelet count, and WBC differential count (neutrophils, bands, lymphocytes, eosinophils, basophils, monocytes, and other cells).

[figure not shown]
Appendix 4

[figure not shown]
Schedule of Assessments: Safety Follow-Up Period (cont)

[figure not shown]

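### The open-label schedule marks a 14th study-drug dose at Week 104, a visit the protocol defines as 4 weeks after the last of 13 doses

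*Combined protocol and SAP*

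**What the plan says.** Protocol Section 4.3.3.1 states the open-label dose count for Cohort A: "an additional 52 weeks of open-label lebrikizumab (13 doses"). Section 3.1.1 sets the interval at 4 weeks and refers the reader to Appendix 2 for the open-label assessments.

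In Appendix 2, the row "Study drug administration" is marked in all 14 visit columns from Week 52 (Day 1 OL) to Week 104 (Week 52 OL). The Week 104 column is headed EoT/SFU Wk4. SAP Appendix 3 reproduces the same row, so this is one error carried over, not two.

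Four other statements fix what the Week 104 visit is:

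- Section 3.1.1 places the end-of-treatment visit "approximately 4 weeks after their last dose of study drug".
- Appendix 2 footnote b says this visit replaces Safety Follow-up Visit 1, and continues: "The next visit is Safety Follow-up Visit 2 at Week 12 (12 weeks after last dose of study drug").
- Appendix 4 times its visits by "WEEK post last dose" (4, 12 and 18), and footnote a says of the first that, for patients completing the open-label period, "the Week 52OL will count as this visit".
- Section 3.2 expects the last patient's last visit "a maximum of 118 weeks after the last patient is enrolled and randomized into Cohort A", with 18 weeks of safety follow-up after the last dose.

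**The concern.** A visit cannot be both a dosing visit and the visit 4 weeks after the last dose. The schedule of assessments is what site staff work from. No statement says whether Section 4.3.3.1 or Appendix 2 prevails if they differ.

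Followed as written, the table adds a 14th dose at a visit that already counts as Safety Follow-up Visit 1, and the patient then has no visit 4 weeks after the true last dose. Depending on how the site times the remaining visits, either follow-up runs later than planned or the 18-week safety window is cut short. In the second case the final antibody sample, which Section 5.1.3 times to allow drug washout, is also taken closer to the last dose than intended.

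**Working it through.** **Inputs.** 13 open-label doses (Section 4.3.3.1); 250 mg every 4 weeks, first open-label dose at Week 52 (Section 3.1.1, Appendix 2); safety visits 4, 12 and 18 weeks after the last dose (Appendix 4); 118-week maximum to last visit (Section 3.2).

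**The text's own figure.** Dose 13 falls at 52 + 12 × 4 = Week 100. End of treatment, 4 weeks later, is Week 104. The last safety visit is 100 + 18 = Week 118, which equals 52 + 52 + 14 and matches the stated maximum. The text is internally consistent with 13 doses.

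**The table's figure.** Columns from Week 52 to Week 104 number (104 − 52)/4 + 1 = 14, and all 14 carry a drug mark. Dose 14 is at Week 104.

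**Is the mark a column shift in the extracted table?** Unlikely. The row has 16 cells: 14 marks, then blanks under early termination and unscheduled visit. The concomitant-medication row has a blank under Week 52 Day 1 OL and marks in every later column, so the columns align. The SAP copy shows the same pattern.

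**Comparison with the blinded schedules.** Appendix 1 and Appendix 3 mark the drug row at Weeks 0, 4, …, 48, which is 48/4 + 1 = 13 doses, and leave the Week 52 end-of-treatment column blank. This agrees with Section 3.1.1: "at least 13 doses (one dose every 4 weeks [Q4W]) of blinded treatment over 48 weeks". The open-label numbered visits run from 35 to 47, which is 47 − 35 + 1 = 13; the Week 104 column has no visit number. The Week 104 mark is the exception.

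**Consequence for follow-up.**

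| | Last dose | Visit 1 | Visit 2 | Visit 3 |
|---|---|---|---|---|
| Intended (4/12/18 weeks after dose) | Week 100 | Week 104 | Week 112 | Week 118 |
| Dosed at Week 104, visits timed from that dose | Week 104 | due Week 108, none scheduled | Week 116 | Week 122 |
| Dosed at Week 104, visits kept tied to Week 104 | Week 104 | Week 104 (0 weeks after dose) | Week 112 (8 weeks after) | Week 118 (14 weeks after) |

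In the second row the first post-dose visit is 12 weeks after the dose, and the last is 122 − 118 = 4 weeks past the stated maximum. In the third row the last visit is 18 − 14 = 4 weeks short of the required follow-up.

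**Dose.** 13 × 250 = 3250 mg; 14 × 250 = 3500 mg.

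**The case against.** The strongest reply is that this is one stray mark that a careful reader can resolve. The column is labelled end of treatment and follow-up Week 4, only 13 visits are numbered, and Section 4.3.3.1 gives the count. Section 4.2 says the IxRS assigns open-label kits, so drug may not be released from this table at all. This bears on likelihood and weight. It does not remove the contradiction, and the documents do not say how many open-label kits the IxRS releases; it could have been configured from the same table.

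The size can also be challenged. The 118 weeks is an expected time counted from randomization of the last Cohort A patient, not a limit for each patient (the synopsis allows up to 2.9 years, about 2.9 × 52 = 151 weeks). The comparison with Week 122 therefore bites only for the last patients randomized. Follow-up ending 14 weeks after the dose would require ignoring the explicit 18-week rule. One more 250 mg dose is small where Section 4.3.3.1 already allows some patients up to 31 blinded doses. These points stand, and they are why the follow-up results are given as alternatives.

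Timing matters too. SAP Section 2 gives 8 April 2015 as the end of Cohort A enrollment, and SAP Version 2 was signed on 13 September 2017. If the last patient was randomized by that date and entered open label at Week 52, Week 104 fell in early April 2017. Correcting the SAP copy would then change no dosing. Protocol Version 7, however, reports the August 2016 interim analysis and the decision to continue the Cohort A extension, so its table could still have been in use.

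**Conclusion.** The contradiction is real, and the error is the Week 104 mark in protocol Appendix 2: 14 doses in the table against 13 in the text. Week 100 is the intended last dose; the dose count, the definition of the visit, the follow-up timing and both blinded schedules all agree on it.

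The effect is limited to Cohort A patients actually dosed at Week 104. Their number is not given; Section 5.1.1.1 reports 78 + 76 = 154 treated in Cohort A, and only those who entered open label and reached that visit could be affected. For each, the cost is one unplanned 250 mg dose, no 4-week post-dose visit, and later safety visits that are either delayed or 4 weeks too close to the dose. Appendix 2 requires assessments before dosing on treatment days, so Week 104 assessments and samples stay valid as about 4 weeks after the Week 100 dose. The week numbers assume open label starts at Week 52. The 52-week primary analysis is unaffected. The correction should be made because the table is an operational dosing instruction and is wrong as written.

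**What to change.** Delete the Week 104 study-drug mark in protocol Appendix 2 and in its copy, SAP Appendix 3, so that open-label dosing ends at Week 100 with 13 doses. Confirm that the IxRS releases no open-label kit at Week 104, and notify sites. Check the dosing records; for any patient already dosed at Week 104, time the 4-, 12- and 18-week safety visits from that dose (Weeks 108, 116 and 122).

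The cost is one mark in each of two tables, an IxRS and dosing-record check, and a site notice.
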